22. Covariate: Parent acculturation will be assessed using the previously validated 24-item Bidimensional Acculturation Scale for Hispanics. This scale consists of 3-subscales including language use, linguistic proficiency, and electronic media, which are combined into Hispanic and non-Hispanic domains.^{116,117} This scale had acceptable internal consistency (alpha=0.90 and 0.96 for Hispanic and non-Hispanic domains, respectively).¹¹⁶ Validity coefficients for the combined scale with generation status and the Short Acculturation Scale for Hispanics were high among the Mexican American and Latin American US sample.¹¹⁶ Child acculturation will be estimated using proxy measures, including country of origin, years living in the US, and preferred language(s), which have been associated with Latino preschoolers' risk of obesity.⁴²

23. Covariate: COVID-19 Questionnaire. Derived from the World Health Organization's questionnaire on behavioral insights research for COVID-19, and supplemented by additional questions relevant to our population from the 2020 Household Pulse Survey (U.S. Census Bureau), and Connor Davidson Resilience Scale 2-item. Including a COVID-19 questionnaire will allow us to adjust for how the pandemic affects both arms of the study. This may be an important covariate for physical activity and screen time outcomes given that social distancing and other stressors of the pandemic may affect mobility.

Process evaluation. We will conduct a process evaluation of the curriculum to track and ensure proper dose and fidelity across the three sites and four intervention years.⁹⁵ This process evaluation will include assessment staff directly observing class sessions and tracking teaching staff-student interactions and participation via a standard checklist. This checklist will include a measure of class time spent on each lesson, the number of children participating in the lesson with a particular emphasis on time spent on role-playing activities and reinforcement by teachers, the number of children completing lesson activities, and the number of children and parents completing take-home activities. We will also track resources used during lessons. The process evaluation's assessment of role playing in particular will provide several measures of the curriculum's application of Social Learning Theory.⁹⁶

Role playing will directly measure modeling of behaviors by the preschool teachers for the children.⁹⁷ It will provide a measure of the children's rehearsal of behaviors, which facilitates retention of the behavior. It will also measure the number of times a teacher provides reinforcement in the form of positive prompts or praise during these behavior rehearsals. Finally, parent participation in the take home materials/lending library will be logged and also tracked by collecting assignments completed by the parent and children at home.

Post-Intervention Qualitative Interviews. We will conduct 40 semi-structured, qualitative interviews with intervention participant parents after Time 3 assessments are completed. We will follow standard qualitative procedures for data collection and thematic analysis.^{172,173} Interviews will explore acceptability of the Fit 5 Kids intervention and how to improve intervention efficacy. Participants will be randomly selected with balanced representation from both the intervention and control groups, and even distribution across head start centers. If there is a low response (less than 60%) to the initial invitation to complete an interview at any center, a second round of invitations will be sent to remaining parents until at least 80% of the target interviews for that center are completed.

A standardized interview script will be developed and consist of general open ended questions, followed by detailed probes and prompts to explore questions of interest. Interviews will be audio recorded, transcribed, verified, and translated (if necessary). We will use NVIVO, a qualitative software analysis program, to facilitate data coding, retrieval, and analysis. The statements in the interviews will be organized by specific questions. Using verbatim statements, each unit will be assigned a broad category and specific codes to facilitate data retrieval and analysis overall, by specific sub-categories, and participants' characteristic groups.

The multilevel Fit 5 Kids intervention consists of the classroom curriculum, weekly parent newsletters, in-person (or by telephone) goal setting on their child's screen time, a lending library of resources (books, games, arts/crafts, etc), private parent Facebook group, and text messages on screen time parenting practices offered over 7-8 weeks in the Fall semester. There will also be two "booster" weeks of classroom activities, daily parent newsletters, goal setting, and daily text messages on screen time parenting practices offered during the booster weeks in the Spring semester. The classroom component will be taught by bilingual (English/Spanish) research staff interventionists. Parent newsletters, goal setting, and text messages will be offered in English and Spanish per parent preference. The lending library of resources for parents/children will be available throughout the entire school year.

The elements unique to the proposed study include: 1) questionnaires, 2) physical activity (PA) and screen time data, 3) the Fit 5 Kids intervention, and 4) qualitative data, i.e., post-intervention qualitative interviews.

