8. Facebook – Similar process. However, we will further utilize Facebook as a platform to distribute video lessons to participants, post the newsletters, post pictures of the activities being mailed home, share information for attending the digital lives, and post the parent engagement questions from the goal setting form as another way to gauge their engagement in the remote intervention. This content will also be available to participants outside of Facebook.
9. Booster Weeks – If booster weeks are done remotely, we will follow similar procedures as outlined above. Like the in-person version of the booster weeks, parents will still receive a newsletter and text message tip daily (for each lesson). There will be 5 video booster lessons, and we will mail home activities for 4/5 of them. Parents will be invited to attend an optional Digital Live. We will set goals once for the booster week(s) period, and will still post the same type of content on Facebook.

Control condition: The control centers will not implement Fit 5 Kids but will instead provide their children with the standard Head Start preschool curriculum. This standard curriculum typically provides brief advice on healthy eating and active living, but does not go into detail about screen time reduction. As this is the standard practice of Head Start programs, there are no ethical issues to consider with the control participants.

Measurement Procedures. The investigators have experience with all proposed questionnaires and accelerometry among Latino families, ensuring high scientific rigor. All assessments and surveys measuring mediating, moderating and outcome variables as well as covariates will be assessed immediately pre-intervention (Time 1, i.e., September/October of each year), immediately after the classroom intervention (Time 2, i.e., January of each year), and 8-months after starting the

intervention (Time 3, i.e., May/June of each year). The Time 2 measurement is necessary in order to detect changes in mediators (e.g., parenting practices and parent self-efficacy) that will be expected to change prior to outcomes such as BMI z-score. The Time 2 measurement will allow for mediation analyses to better describe mechanisms underlying changes in outcomes.⁹⁸ The dietary assessment by Food Frequency Screener will occur at Time 1, Time 2, and Time 3. Research staff will collect socio-demographic and anthropometric measurements on the children and parents at their assigned Head Start center.

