12. Mediating variable: Screen time (media) parenting practices. The screen time parenting practices scale, also called the TV Parenting Practices scale, consists of 15-items with the following responses: never, rarely, sometimes, or often.⁶⁶ Our team has validated these questions among Latino families, including preschool age children. Screen time parenting practices will be a mediator for the relationship between the intervention and changes to screen time.⁶⁷

13. Anthropometric outcome: BMI z-score. Study staff will measure height and weight per standard NHANES protocol.¹²⁴ A portable stadiometer will be used to measure height (to nearest 0.1 cm), and an electronic scale to measure weight (to nearest 0.1 kg). Duplicate measures will be taken with the mean recorded as the value. A third measurement will be taken if there is >0.2 cm or 0.2 kg difference; the two closest values will be used to calculate the mean value. BMI (kg/m²) will be calculated and BMI z-scores will be determined based on 2000 CDC growth charts⁹⁹ as per the Expert Committee Recommendations for assessment of overweight and obesity among 2-19 year olds.¹²⁵

14. Behavioral outcome: Dietary intake by Food Frequency Screener. The preschool children's usual dietary intake over the past 6 months will be measured by the Block Kids Food Frequency Screener as reported by their parents, and screener data will be processed by NutritionQuest (Berkeley, CA), an international leader in dietary assessment and analysis. The Block Kids FFQ, available in English and Spanish, has been validated compared to 24-hour dietary recalls among children, and yielded significant correlations for energy intake ($r=0.43$), % energy from fat ($r=0.51$), % energy from carbohydrates ($r=0.69$), % energy from protein ($r=0.55$), dairy servings ($r=0.74$), and fruit servings ($r=0.52$).⁵⁶ The Block Kids FFQ estimates of fruit and vegetables significantly correlated with the objective biomarkers of children's serum carotenoids and skin carotenoids.^{56,102} Total dietary energy intake will be a behavioral outcome of interest. [name] has led and/or substantially contributed to multiple nutritional epidemiological studies among children.^{85,126-133}

15. Exploratory behavioral outcomes: fruit and vegetable intake and skin carotenoids.

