Skin carotenoids are an objective biomarker of fruit and vegetable intake in children and adults, and are responsive to changes in carotenoid intake from fruits and vegetables.¹⁰⁰ Skin carotenoids have been validated against plasma concentrations of carotenoids as reviewed,^{100,139} Dietary intake of carotenoids as estimated by the Block Kids FFQ was significantly correlated ($\beta=0.87$, $p=0.02$) with skin carotenoids among a diverse sample of children (59.8% Latino, 25.7% Black).¹⁰² Similarly, dietary intake of total fruit ($r=0.21$), total vegetables ($r=0.32$), and total carotenoids ($r=0.40$) estimated by the Block Kids FFQ among preschoolers was significantly ($p<0.05$) correlated with skin carotenoids.⁵⁶ Skin carotenoids measurements are taken on the palm of participants' hands, where skin melanin is found at their lowest concentrations and do not bias results.^{101,102} We will use the commercially available instrument, "BioPhotonic Scanner" (Pharmanex Global Research, Provo, UT), which was used in a previous pediatric validation study.⁵⁶ Two instruments will be provided free of charge by Pharmanex (see letter of support by [name]), along with training and technical support. The Seattle and Central Valley sites in Washington State will share one instrument while the Houston site will use the other to measure preschoolers' skin carotenoids per a standard protocol at Times 1, 2, and 3. Measurements will also be compared to fruit and vegetable intake estimated by the Block Kids Food Frequency Screener, as further validation of the Food Frequency Screener among Latino preschoolers. Skin carotenoids will be an exploratory objective outcome for the present study, similar to fruit and vegetable intake via the Block Food Frequency Screener.

Table 1. Summary of study variables

Variable	Instrument	Variable type	Validation and other study references	Investigators with expertise
Screen time	Screen time diary (7-day)	1 ^o outcome	40,41,54	[name]

Model of Goal Directed Behavior	Attitudes (15-item) Perceived Positive/Negative Behavioral Control (17-item) Subjective Norms (9-item) Positive and Negative Anticipated Emotions (29-item) Habits (9-item) Self-efficacy (14-item) Desires (7-item) Intentions (10-item)	Mediator	40	[name]
Parent outcome expectations for limiting screen time	POETV (25-item)	Mediator	68-70	[name], [name]
Screen time parenting practices	Screen time parenting practices (15 items)	Mediator	66,67	[name], [name], [name]

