32.0 Drugs or Devices

We will be using the commercially available instrument, "BioPhotonic Scanner" (Pharmanex Global Research, Provo, UT) to provide an objective assessment of fruit and vegetable intake via skin carotenoids. This is an exploratory outcome; we will simply examine correlations with fruit/veg intake, as a means of quality control. This is not meant to be FDA device validation, nor will it be presented as such. Additionally, we have cited several pediatric studies that have also used the device without the requirement of registering it with the FDA

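### The Screener–carotenoid check uses one scanner per region with no scanner or site adjustment, so a simple correlation across sites can be shifted by a calibration difference

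*Combined protocol and SAP*

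**What the plan says.** Section 9.0, item 15, assigns the two skin carotenoid scanners by region: "The Seattle and Central Valley sites in Washington State will share one instrument while the Houston site will use the other". They are used "to measure preschoolers' skin carotenoids per a standard protocol at Times 1, 2, and 3", and the manufacturer supplies them "along with training and technical support". Neither cross-calibration nor reading the same children on both scanners is mentioned.

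The same item then gives the readings a second use: "Measurements will also be compared to fruit and vegetable intake estimated by the Block Kids Food Frequency Screener, as further validation". Section 32.0 describes the analysis in one clause: "we will simply examine correlations with fruit/veg intake, as a means of quality control".

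Neither section says whether the correlation is computed within site or scanner, or which visits it uses. Carotenoids are read at all three visits, and section 9.0 adds that "The dietary assessment by Food Frequency Screener will occur at Time 1, Time 2, and Time 3", so paired values will exist at each visit. Section 11.0 sets out mixed models for screen time, BMI z-score, energy intake and MVPA but no model for this comparison. It does state that randomisation is by centre and stratified by site.

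**The concern.** All Washington children are read on one device and all Houston children on the other, so a calibration difference between devices cannot be told apart from a regional difference in carotenoids. The analysis named, a simple correlation, has nothing to absorb that difference.

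The regions were chosen to differ: section 20.0 describes urban and suburban Seattle, the rural Central Valley and urban Houston. A regional difference in fruit and vegetable intake is therefore plausible, although the documents do not quantify one. If it exists, it combines with the scanner offset and adds a between-region component to the correlation that says nothing about how well the Screener ranks children. Scanner is also partly tied to wave, because section 9.1 enrols only Seattle centres in year 1.

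At stake is how the fruit and vegetable correlation is read, both as further evidence for the Screener in Latino preschoolers and as quality control for the readings. The correlations that item 15 cites are modest (0.21 for fruit, 0.32 for vegetables, 0.40 for total carotenoids), so a shift of 0.05 to 0.13 would change the impression given.

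**Working it through.** The plan states no target correlation, precision or sample size for this check, so there is no figure to reproduce. The question is how far a simple correlation across sites can move.

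**Inputs from the documents**
- Within-site correlation r: 0.21 (fruit) and 0.32 (vegetables), the values cited in section 9.0, item 15, used as illustrative true values.
- Houston share p: section 20.0 gives 8 + 6 + 6 = 20 centres, so p = 6/20 = 0.30. With ten Seattle centres (section 26.0) the total is 22 and p = 6/22 = 0.27.
- Enrolment: 280 dyads (section 4.0).

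**Assumed inputs (not in the documents)**
- d, the scanner offset, and g, the Houston–Washington gap in reported intake, both in within-site SD units.

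**Formula.** For two groups with common within-group correlation r and unit SDs, with v = p(1 − p):

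pooled r = (r + v·d·g) / √[(1 + v·d²)(1 + v·g²)]

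Here v = 0.30 × 0.70 = 0.21.

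**Worked case:** r = 0.32, d = 1, g = 0.5.
- Denominator: √(1.21 × 1.0525) = 1.1285.
- Same direction: (0.32 + 0.105) / 1.1285 = 0.377.
- Opposite direction: (0.32 − 0.105) / 1.1285 = 0.191.

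| Offset d | Gap g | From r = 0.21 | From r = 0.32 |
|---|---|---|---|
| 0.5 | 0 | 0.205 | 0.312 |
| 1 | 0 | 0.191 | 0.291 |
| 0.5 | 0.5, same direction | 0.249 | 0.354 |
| 0.5 | 0.5, opposite | 0.150 | 0.254 |
| 1 | 0.5, same direction | 0.279 | 0.377 |
| 1 | 0.5, opposite | 0.093 | 0.191 |

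With p = 0.27 the d = 1, g = 0.5 results for r = 0.32 are 0.374 and 0.197, so the inconsistent centre counts do not matter here.

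**Two features of the result**
- An offset alone (g = 0) only attenuates. An upward shift needs an intake gap in the same direction as the offset.
- With a true correlation of zero and d = g = 1, the pooled value is 0.21/1.21 = 0.17, above the two-sided 5% critical value of 0.117 at n = 280. That is an extreme case.

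**Check of the remedy.** In a simulation of 200,000 children with r = 0.32, d = ±1 and g = 0.5, the simple correlation was 0.379 or 0.191. Centring both measures within scanner gave 0.322 in both cases.

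**Sampling error.** The Fisher-z 95% interval at n = 280 is 0.21 to 0.42 for r = 0.32 and 0.10 to 0.32 for r = 0.21, before any widening for centre clustering. Treating three visits as independent (3 × 280 = 840 records) would narrow the first to 0.26 to 0.38. That narrowing would be false precision, because each child contributes up to three correlated pairs.

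**The case against.** The best defence is that the plan is brief here rather than wrong. It does not say that scanners or visits are pooled, a standard protocol and manufacturer training are in place, and section 11.0 says in general terms that analyses respect children nested in centres. The size rests wholly on assumed inputs. With a 0.5 SD offset, the shifted values (0.15 to 0.25 for fruit, 0.25 to 0.35 for vegetables) lie inside the sampling interval at n = 280. No threshold or decision depends on the correlation.

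Most of this stands, and it limits the point to a small improvement. It does not remove it. Section 32.0 names a simple correlation, section 11.0 does not cover this comparison, and the shift is systematic, so more children would not average it out.

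A reader might also infer that post-intervention visits make the correlation spurious. The documents do not support that: no visit is named for the comparison, and a real change in both intake and carotenoids is signal. If all visits were pooled, with the intervention arm at Times 2 and 3 forming one third of arm-visits, a reporting-only shift of 0.5 SD would move 0.32 to 0.31. The other patterns tried gave 0.29 (opposite shifts of 0.5 and 0.2 SD) and 0.36 (equal 0.5 SD shifts), so the effect is about 0.01 to 0.04. The firmer visit issues are the repeated readings per child and the recall window. The Screener covers "usual dietary intake over the past 6 months", so at Time 2 in January it reaches back before Time 1 in September/October.

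**Conclusion.** The point holds as a minor one. Scanner is fully aliased with region, no cross-calibration is described, and the stated analysis has no scanner or site adjustment. A calibration difference alone would attenuate a simple correlation across sites (0.32 to 0.29 at 1 SD). Combined with a 0.5 SD regional intake gap, it would move 0.32 to 0.38 or 0.19 at a 1 SD offset, and to about 0.35 or 0.25 at 0.5 SD. The offset and the gap are assumptions; the true bias could be nil.

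Three stronger readings should be resisted:
- **Arm comparisons of carotenoids are confounded by scanner.** They are not: stratification by site protects them.
- **The energy intake outcome is undermined.** It is not: the comparison concerns fruit and vegetable intake only, and energy intake has separate support in section 9.0, item 14 (r = 0.43 against 24-hour recalls).
- **The Screener's validity rests on this check.** It does not: section 9.0 calls it further validation and cites earlier comparisons with recalls and with serum and skin carotenoids.

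**What to change.** Replace the simple correlation with one computed within scanner:
- **Adjustment.** Use a partial correlation between Screener fruit and vegetable intake and skin carotenoids, adjusted for site (which contains scanner) and wave. Alternatively, estimate it separately for Washington and Houston and combine the two.
- **Visits.** Make Time 1 the main estimate. If all visits are to be used, fit a site-adjusted model with child and centre effects, so that repeated readings are not counted as independent.
- **Reporting.** Give the Washington and Houston estimates side by side, and report any cross-calibration of the scanners that was done.

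This is a change of analysis wording and needs no new measurements; section 30.0 indicates that participant activities are complete and analysis remains open. There are two costs. Any true Houston–Washington covariation is set aside, but this design cannot separate it from a scanner offset. A Time 1 estimate uses up to 280 pairs and forgoes information on responsiveness to change, which the all-visit model would keep.

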7.0 Study Timelines

- 7.1 Participants enrolled in the study will participate for the duration of the school year (approximately 8 months).
- 7.2 We expect to enroll participants in 4 waves. All participants will be enrolled by end of calendar year, 2021. The final wave of participants will finish in June of 2022.
- 7.3 We expect analysis to be completed by end of calendar year, 2023.

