11.0 Data Analysis/Management

We will conduct intent-to-treat analyses. Children will be the unit of analyses, although analyses will recognize the hierarchical nature of the data, i.e., time points nested within children, and children nested within Head Start centers. Randomization at the center level with stratification by study site should balance many observed and unobserved confounders at the center and child levels. For the primary (screen time) and other outcomes (BMI z-score, dietary energy intake, and MVPA), two sets of analyses will be performed. The first set of analysis will be separate cross-sectional analysis of T2 and T3 outcomes respectively. Given the nested structure of the data, we will apply mixed effects regression models¹⁵⁶ to examine the effects of the intervention on each outcome while controlling for unbalanced covariates and account for correlations due to clustering. In the second set of analysis we will conduct a repeated measure analysis using outcomes from all 3 time points. For Hypothesis 2, we will assess the extent through which parent outcome expectations, self-efficacy, and screen time parenting practices exert their influence on (i.e., mediate) change in screen time via the intervention. We will use a structural equation modeling (SEM) approach^{157,158} specifically, we will evaluate mediation by decomposing a total effect on the screen time slope into direct effects and indirect effects. The indirect effects represent the influence of the intervention on change in screen time via parent outcome expectations, self-efficacy, or screen time parenting practices. We will test the moderation relationships of Hypothesis 3 using mixed effects regression models as outlined for Hypothesis #1.

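### The outcome models omit the wave in which centers are randomized, and the COVID-19 covariate is proposed without fixing which measurement may be used or how waves without a baseline value are kept

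*Combined protocol and SAP*

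**What the plan says.** Section 9.1 describes four waves: two Seattle centers in year 1, then two centers in each of three regions in each of years 2 to 4, enrolled for randomization to intervention or control. Section 7.0 gives the calendar: "We expect to enroll participants in 4 waves. All participants will be enrolled by end of calendar year, 2021", with the last wave finishing in June 2022. Baseline falls in autumn ("Time 1, i.e., September/October of each year").

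Item 23 of Section 9.0 lists a COVID-19 questionnaire as a covariate. It combines WHO material, a two-item resilience scale and "additional questions relevant to our population from the 2020 Household Pulse Survey". Its stated purpose is: "Including a COVID-19 questionnaire will allow us to adjust for how the pandemic affects both arms of the study". The commitment is conditional: "This may be an important covariate for physical activity and screen time outcomes".

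On timing, Measurement Procedures in Section 9.0 says: "All assessments and surveys measuring mediating, moderating and outcome variables as well as covariates will be assessed immediately pre-intervention". The same sentence adds a second round in January and a third in May/June.

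Section 11.0 specifies mixed models at Time 2 and Time 3 and a repeated-measures model, "while controlling for unbalanced covariates and account for correlations due to clustering". It mentions stratification of the randomization by site. It does not mention wave or school year, the COVID-19 questionnaire, the time point at which any covariate is taken, or what to do when a covariate is absent for a whole wave.

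**The concern.** The pandemic reaches this trial mainly through calendar time, and calendar time is the wave. Wave is known for every child, cannot be altered by treatment, and is part of the grouping in which centers are randomized. The plan leaves it out and points to a parent-reported score instead. That score has two weaknesses.

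- **It is also measured after the intervention.** The intervention includes repeated parent contact, goal setting, an optional parent support group and home activities. These could plausibly change answers about behavior, stressors and resilience. Under a rule that adjusts for whatever is unbalanced, an answer that treatment has moved is the one most likely to be selected. Conditioning on it can remove part of the effect or distort it.
- **It has no baseline value in any wave that began before 2020.** A standard complete-case fit would silently drop those centers, and the result would no longer describe all randomized centers, as Aim 1 requires.

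**Working it through.** **1. The plan's own figure.** Section 11.0 needs 240 participants at Time 3 with about 15% attrition. 240 / (1 − 0.15) = 282.4, so 283. The stated approximate 280 is reproduced. Power cannot be reproduced, because the plan gives no alpha, target power, effect size, SD or intracluster correlation.

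**2. Centers per wave (Section 9.1).** 2 + 6 + 6 + 6 = 20. Section 20.0 agrees (8 + 6 + 6 = 20). Section 3.0 says 22, and Section 26.0 gives ten in the Seattle area (10 + 6 + 6 = 22). I use 20 and assume equal size: 280 / 20 = 14 dyads per center at Time 1 and 240 / 20 = 12 at Time 3.

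**3. Waves with Time 1 before 2020.** Three readings are open:

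| Reading | Time 1 of waves 1–4 | Waves before 2020 | Centers | Dyads |
|---|---|---|---|---|
| Count back from Section 7.0 | 2018, 2019, 2020, 2021 | 2 | 8 of 20 (40%) | 8 × 14 = 112 |
| Wave 1 in autumn 2019 | 2019, 2020, 2021, 2022 | 1 | 2 of 20 (10%) | 2 × 14 = 28 |
| Wave 1 in autumn 2020 | 2020, 2021, 2022, 2023 | 0 | 0 | 0 |

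The second reading fits Section 30.0, which has participants enrolled in 2022, but not Section 7.0. The third also contradicts Section 7.0. The timeline table in Section 1.0 has calendar headings starting in 2019, and in the text available its columns are too broken to date a wave. These are incompatible schedules, not the two ends of one range.

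A wave begun in autumn 2019 would reach Time 3 in May/June 2020. It lacks a baseline value, but not necessarily every value.

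**4. Cost of a complete-case fit.** For a two-arm comparison of equal-sized centers, the minimum detectable effect is proportional to (t₀.₉₇₅ + t₀.₈₀) / √c on c − 2 degrees of freedom, with c centers. The ratio does not depend on the intracluster correlation. The 80% starting power is an assumption.

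- c = 20: 2.963 / √20 = 0.6625.
- c = 18 (one wave lost; 252 dyads at Time 1, 216 at Time 3): 2.985 / √18 = 0.7035, ratio 1.06. Power of 80% falls to about 75%.
- c = 12 (two waves lost; 168 and 144): 3.107 / √12 = 0.8970, ratio 1.35. Power of 80% falls to about 54%.

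**5. Is a loss or a bias unavoidable?** A simulation used 20 centers of 12, two pre-pandemic waves, no residual center variance and assumed effects, so its sizes are illustrative only.

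- A Time 1 score set to zero in pre-pandemic waves, with fixed effects for each within-wave center pair, kept all 240 children. It estimated −0.344 against a true average of −0.346 (SE 0.134).
- A complete-case fit kept 144 children. It estimated −0.308 against −0.310 in those waves (SE 0.173).
- Adding a Time 2 score that treatment had shifted gave −0.395 against −0.310. The assumed indirect path was 0.3 × 0.3 = 0.09, and adjustment removed nearly all of it. The direction depends on the assumed signs.

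So neither problem is forced, but both are open under the plan's wording.

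**6. Price of a wave term.** With 20 centers, three wave terms take center-level degrees of freedom from 18 to 15. The multiplier goes from 2.963 to 2.998, a ratio of 1.012. Wave pays for itself once it explains more than 1 − 1/1.0117² ≈ 2.3% of the variance among center means. Two site terms as well leave 13 degrees of freedom: 3.031 / 2.963 = 1.023 if neither factor explains anything.

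**The case against.** The strongest reply is that the plan does not commit to this adjustment. Item 23 says only that the questionnaire allows adjustment and may matter, and Section 11.0 never names it. Collecting a covariate three times does not mean that the later values enter the arm comparison. Remote delivery is also provided for, so the questionnaire is not the plan's only response to the pandemic. All of this stands. It makes the problem an open rule rather than a declared error, but a rule based on observed imbalance still lets a treatment-shifted answer in.

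A reader might infer four stronger things that the documents do not support:

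- **That the adjustment must either drop early waves or condition on post-randomization answers.** A Time 1 score with a structural zero and wave terms does neither.
- **That 10% to 40% of the sample lacks a baseline value.** Those figures come from schedules that contradict each other, and zero is also a reading of the damaged timeline table.
- **That the protocol expects large year-to-year differences.** Item 23 says only that distancing and other stressors may affect mobility. No between-year variance is given.
- **That leaving wave out biases the comparison.** If each site-wave pair has one center per arm, both arms share the same period and the loss is mainly precision. Section 9.1 suggests this split but does not state it, and Section 11.0 mentions stratification by site only.

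Two further limits are fair. Time 1 is described as pre-intervention, and the documents do not say that it precedes randomization. Wave also cannot capture differences between families within a year, which is what the questionnaire targets; that is a reason to keep it as a sensitivity analysis.

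**Conclusion.** The concern holds in limited form. The models omit a factor that the design largely balances. The one stated adjustment rule could admit a post-intervention COVID-19 answer because treatment had shifted it, and nothing says how waves without a baseline score are retained.

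The size depends on facts that the documents leave unsettled. If two waves began before 2020 and were dropped, the detectable effect would be 1.35 times larger; with one wave, 1.06 times; with none, there is no loss. These ratios assume 20 equal centers. The bias from a Time 2 or Time 3 answer is real in kind, but its size cannot be estimated from the documents. The precision gain from wave is likewise unknown, though the break-even is low at about 2.3% of between-center variance.

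This should be changed before the analysis is run. It does not invalidate the design.

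**What to change.** In Section 11.0:

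1. Include site and wave (school year) as fixed factors in the Time 2, Time 3 and repeated-measures models for every outcome, whatever the observed balance.
2. State that Time 2 and Time 3 COVID-19 answers are not covariates in the arm comparison. They may be reported descriptively.
3. Use the Time 1 COVID-19 score only in a sensitivity analysis that keeps waves without it, for example by a structural zero together with the wave terms.
4. Give the actual Time 1 dates of each wave, reconciling Sections 1.0, 7.0 and 30.0. Reconcile the center counts (20 in Sections 9.1 and 20.0; 22 in Section 3.0; ten for Seattle in Section 26.0). State whether each site-wave pair was split one center per arm.

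No new data are needed. The price is about three center-level degrees of freedom for wave (18 to 15 with 20 centers, before site terms), roughly a 1% larger detectable effect if wave explains nothing.
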